Other Safety-Related Reports. At quarterly intervals, the DSMB will also receive unblinded summary reports of treatment retention and reasons for drop-out, by treatment arm and study phase.

Study Stopping Rules. If at any time during the course of the study, the DSMB judges that risk to participants outweighs the potential benefits, the DSMB shall have the discretion and responsibility to recommend that the study be terminated.

Monitoring of Data Quality by the DSMB. At least on a quarterly basis during the course of the study, the DSMB will receive a report on data quality and completeness. [name] (study biostatistician) will prepare these reports in collaboration with [name]. At a minimum, this will include an overview of the progress of patient intake and retention; summary reports describing patient compliance with evaluations as described in the protocol; and a summary of the completeness and quality of key data elements needed to characterize patients, study interventions, and primary and secondary outcomes. These reports will be used by the DSMB to evaluate the capacity of the data capture and processing to support scientifically valid analyses.

Annual DSMB Report to NIH/NHLBI. During the course of the study, the DSMB will prepare annual summary reports (two reports in total) of its findings regarding safety and quality based on data received to that point in the study. If there are more specific concerns about data quality, study safety, or other issues, the DSMB can elect to generate reports more frequently. This report will include a summary of all safety findings, as well as an assessment of protocol compliance and data quality. Any recommendations to improve patient safety, protocol adherence, or data quality will be made in this DSMB report. A copy of this DSMB report will also be sent to the PHS IRB along with the annual renewal report.

In addition to the work of the DSMB, the research team will meet on a weekly basis to review study progress. During these weekly meetings, the principal investigator will review informed consent documents, study forms, and procedures completed that week. The study team

will also discuss any procedural difficulties, recruitment issues, and adverse events at this meeting (and before if needed). If there are consistent issues with the logistics, feasibility, or acceptability of recruitment, enrollment, follow-ups, or the intervention (e.g., participant complaints about length of follow-ups), we will review our methods and alter the study protocol as needed.

C. Outcomes monitoring

[name] (PI) will review study outcomes after four participants have completed the trial in order to assess the feasibility and acceptability of exercises and to ensure adequate completion of follow-up measures. If participants' completion or follow-up rates are far below the expected rates, if acceptability scores on the exercises are low, if optimism scores decrease following the exercises, or we sense more generally that some participants have been dissatisfied with the program, we will likely alter the protocol to address these issues. Further, we will preliminarily assess outcome measures after 20 participants have completed the study to ensure the feasibility and acceptability remains adequate and to monitor potential outcomes. We will then complete the more formal data analysis once all 48 participants have completed the trial.

D. Adverse event reporting guidelines

We will follow all PHRC guidelines with respect to reporting unanticipated problems, including adverse events. Specifically, when a serious or nonserious adverse event occurs, the PI will review the event to determine if it was possibly or definitely related to participation in the research. For all unanticipated problems and adverse events deemed related or possibly related to the research, we will complete and submit an Other Event report through Insight/eIRB as soon as possible and within 5 working days / 7 calendar days (as defined in the March 2014 Reporting Unanticipated Problems Including Adverse Events report). At Continuing Review, we will provide a summary of all unanticipated problems as per PHRC protocol. Finally, if there are unanticipated problems, especially if serious or recurrent, the PI ([name]) will amend the protocol if it is deemed necessary to protect the safety and welfare of the participants.

X. References

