PP exercise completion, (b) the utility of ‘booster sessions’ after an initial 8-week intervention, and (c) the relative merits of utilizing PP exercises alone versus an intervention combining PP with MI (PP/MI). Participants completed a minimum of 8 weekly intervention calls, with up to an additional three “booster” calls held every other week (depending on their condition). In these phone calls, participants were asked to complete PP exercises daily or weekly, and may also have received guidance with setting and achieving goals related to physical activity (MI). At 8 and 16 weeks, participants wore an accelerometer to measure their amount of moderate and vigorous physical activity, and also completed a battery of questionnaires assessing psychological outcomes, behavioral adherence, and medical/functional outcomes.

Progress: We have completed enrollment and the obtainment of follow-up data. Though final data analyses are pending, 65% of participants completed at least half of the exercises, and 64% of all exercises were completed. Excluding participants who dropped out prior to completing any exercises, 82% of individuals completed at least half of the exercises, and 76% of all exercises were completed. Though final analyses are pending, we anticipate that booster sessions will be associated with more sustained improvements in psychological and physical health, and the addition of MI will lead to greater improvements in physical activity.

Relevance to proposed study. This study has allowed us to identify which components of the intervention are associated with the greatest improvements in mental health, functioning, and adherence to health behaviors. It also has given us more experience recruiting participants from the inpatient cardiac units, delivering PP and PP/MI interventions, and obtaining information regarding the outcomes we will be examining in this study.

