Other PP intervention studies. We have also completed studies of PP interventions in other populations (e.g., those with psychiatric illness) (PHS IRB #2010P-002826; 2012P-001154; 2012P-002294,). These studies have allowed us to gain further experience in delivering PP interventions in a wide variety of contexts. These additional studies have allowed us to refine the intervention manual for the proposed study by selecting exercises that appear to be most associated with improvements in positive affect, and by adapting the instructions and exercises to make them the most acceptable/relevant to patients’ experiences.

C. Rationale/potential benefits/overview of proposed research

There is clear evidence linking positive emotions with superior cardiac outcomes⁴²⁻⁴⁴ and recent trials have found anhedonia—a lack of interest/positive emotion—to be independently associated with post-ACS mortality^{45,46} Despite this, there has been minimal study of interventions in cardiac patients that specifically focus on the cultivation of positive emotional states. To address this gap in knowledge, we aim to develop a novel PP-based health behavior intervention that is adapted for patients hospitalized for ACS. A treatment cultivating positive emotions in this vulnerable population could provide broad and significant health benefits, and may have distinct—and more powerful—effects than simply attempting to dampen negative emotions.⁴⁷

In the preliminary work noted above, we created and tested a PP-based health behavior intervention in ACS patients and performed a factorial trial to determine which components of the intervention were most effective at improving health behaviors and mental and physical health. Based on this work, we have created an optimized, PP-MI intervention to promote

physical activity. We now plan to test this optimized intervention in a randomized controlled pilot trial in 48 patients recently hospitalized for an ACS.

II. Specific aims

Aim # 1 (primary aim): To assess the feasibility and acceptability of the refined PP-MI intervention in patients who have experienced an ACS.

Hypothesis: The PP-MI intervention will be feasible and acceptable, with $\geq 70\%$ of all exercises completed, self-report follow-up data obtained from $\geq 85\%$ of participants, and physical activity data gathered from $\geq 80\%$ participants.

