It is exceedingly unlikely that a potential participant will be a patient currently in an investigator's clinical practice; however, if an investigator discovers that a potential participant is a member of his/her clinical practice, an alternate investigator will be substituted to provide a description of the study and obtain informed consent.

Finally, once patients sign the consent form, the investigator will perform a focused review of the patient's medical record (including laboratory data) to again confirm that the patient was admitted for ACS, and will consult with the study cardiologist in the event that there is any need for further clarification. If there is question about the patient's medical prognosis (to assess whether the patient has a condition likely to lead to death within 6 months) the study team will consult with the inpatient or outpatient treatment team and the study cardiologist.

Partners Healthcare has an electronic system that lets the participants' study doctors know if they are admitted to a Partners Hospital, or if they visit a Partners Hospital Emergency Department. We will use this system to ensure that the study doctors know about any possible problems or side effects participants experience while taking part in the study.

C. Treatment assignment/randomization

Participants will be randomized to receive the intervention or MI-based health behavior education (control) arm. They will be randomized by a random-number generator and will be assigned a condition after receiving baseline questionnaires when they return to MGH after discharge. The research assistant (RA)/blinded assessor who will conduct the follow ups will be blind to the study condition. The interventionist and subjects will not be blind to the study condition.

V. Study procedures

A. Study visits (See Table 1)

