- (b) Baseline physical activity (prior to hospitalization) will be measured with a modified version of the IPAQ to capture an estimate of the number of minutes spent performing MVPA in the past week (or a typical week, if the past 7 days atypical). The IPAQ has been used and validated in medical cohorts.^{58,59}
- (c) Medication adherence will be measured using the SRMA, a two-item measure of the percentage of time patients report taking their heart medications in the past one and two weeks.
- (d) Dietary adherence to a low-fat diet will be measured with the MEDFICTS scale recommended by National Cholesterol Education Program (NCEP). It is a widely-used and well-validated measure of cholesterol and saturated fat-intake.

Exercise ratings

We will obtain self-report ratings from participants for each completed exercise on two domains (ease of completion, overall utility). Participants will be asked to rate the ease (“how easy was the exercise to complete) and utility (“how helpful was the exercise”) of each exercise on Likert scales of 0-10 (0 = “not easy” or “not helpful,” 10 = “very easy” or “very helpful”).

VI. Biostatistical analyses:

A and B. Specific data variables and study endpoints

Aim 1: (*feasibility, acceptability*; primary aim): To determine whether the PP-MI intervention is feasible and acceptable by participants.

Measures:

- Rates of intervention completion (recorded by study trainer)
- Follow-up completion of self-report and objective adherence measures
- Measures of ease and utility

The intervention will be considered feasible if (1) at least 70% of all exercises are completed, (2) self-report follow-up data is obtained in 85% of participants, and (3) full accelerometer data is obtained in 80% of participants. The intervention will be considered acceptable if participants rate the PP exercises as at least 6/10 on ease and at least 7/10 on utility.

Aim #2 (between-group differences physical activity): To assess which group (intervention or control) is associated with the greatest physical activity at 12 (primary timepoint) and 24 weeks post-enrollment, as measured by self-report International Physical Activity Questionnaire (IPAQ).

Measures:

- Physical activity (IPAQ) (primary health behavior outcome measure)

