Aim #3 (psychological, health behavior, and functional outcomes): To examine the impact of the PP-MI intervention on self-reported adherence measures, psychological outcomes, functioning, and health-related quality of life at 12 (primary timepoint) and 24 weeks post-enrollment.

Measures:

- Self-reported adherence (MOS-SAS)
- Cigarette Use
- Physical activity (IPAQ)
- Medication adherence (SRMA)
- Dietary adherence (MEDFICTS)
- Alcohol Use (AUDIT-C)
- Psychological outcomes:
 - Positive emotions (PANAS)
 - Optimism (LOT-R)
 - State Optimism (SOM)
 - Depression/Anxiety (HADS-D and HADS-A)
 - Stress (PSS-4)
- Medical outcomes:
 - Physical functioning (DASI)
 - Health-related quality of life (SF-12)
 - Cardiac Symptoms (WISE)

C. Statistical methods

Data will be downloaded from REDCap into the Stata statistical package.

For Aim #1 (*feasibility, acceptability*), descriptive statistics will be used to report the proportion of exercises completed and proportion of participants who provided follow-up information.

Descriptive statistics also will be used to determine mean ratings of ease and utility for each exercise. Significance will be set at $p < .05$, using two-tailed statistical tests.

For the Aim #2 analyses (between-group differences in MVPA), we will perform random effects regression analyses with a random intercept for each participant. We will include group, time, and group x time interaction variables and will control for baseline physical activity (as measured by IPAQ). This will allow us to include participants with some missing data.

For the Aim # 3 analyses (between-group differences on psychological, health behavior, functional, and quality-of-life outcomes), we will use a random effects regression model with a random intercept for each participant, as in Aim #2.

D. Power analysis

The study will likely not be powered to definitely test for between-group differences on the secondary outcome, but it should be adequate to generate effect sizes for a larger, multisite efficacy trial by the end of the grant period. We hypothesize that the intervention will have a moderate effect size on physical activity (vs. the control condition), based on similar effect sizes for psychological interventions in cardiac patients.⁹⁵⁻⁹⁷

VII. Risks and discomforts

A. Complications of surgical/non-surgical procedures

No surgical or non-surgical procedures are being used in this study.

B. Drug side effects and toxicities

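### Does the 70% exercise-completion criterion lack a denominator, so that the feasibility verdict turns on whether never-starters are counted?

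*Combined protocol and SAP*

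**What the plan says.** Section VI.A/B, Aim 1 (the primary aim) gives three feasibility conditions. The first is "The intervention will be considered feasible if (1) at least 70% of all exercises are completed". The other two read "2) self-report follow-up data is obtained in 85% of participants, and (3) full accelerometer data is obtained in 80% of participants". The Aim 1 hypothesis in Section II uses the same thresholds, but words the third more loosely: "and physical activity data gathered from" at least 80% of participants. Section VI.C promises descriptive statistics only, namely the "proportion of exercises completed and proportion of participants who provided follow-up information".

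Section I.B, on the factorial trial, reports completion in two ways. For all participants: "65% of participants completed at least half of the exercises, and 64% of all exercises were completed". Then, with a stated restriction: "Excluding participants who dropped out prior to completing any exercises, 82% of individuals completed" at least half, and "76% of all exercises were completed".

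On timing, Section IV.C says that participants "will be assigned a condition after receiving baseline questionnaires when they return to MGH after discharge". Section V.A places the first in-person session directly after randomisation.

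**The concern.** Feasibility is the one aim that this pilot is sized to settle, and it is judged by a threshold. A threshold on a proportion can be applied only if the denominator is known. Neither Section II nor Section VI says whether participants who complete no exercise count as zeros or drop out of the calculation. The team's most recent figures fall on either side of the threshold (64% < 70% < 76%), so the same data could be called feasible or not according to a choice made after the results are seen.

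The second and third conditions raise a similar doubt. Follow-up takes place in both arms at weeks 12 and 24, but the conditions name neither arm nor week, and the primary timepoint is attached only to Aims 2 and 3. Full accelerometer data is not defined. The only wear standard, 5 days of at least 8 hours, is a condition for payment in Section V.A.

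**Working it through.** **Inputs.** Threshold 70% (Section VI). Factorial trial: 64% and 76% of exercises; 65% and 82% of participants completing at least half (Section I.B). At least 48 randomised from up to 80 enrolled (Section III.B). Assumed: 1:1 allocation, so 24 in PP-MI, with 12 exercises each.

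**1. The earlier figures.** No counts are given, so 64% and 76% cannot be rebuilt. The implied share of never-starters is 1 − 64/76 = 15.8% weighted by exercises, and 1 − 65/82 = 20.7% by participants. These are different quantities. Allowing for rounding they span 14.6–17.0% and 19.6–21.8%, which do not overlap if everyone had the same number of exercises. Unequal numbers (8 weekly calls plus up to three boosters) could explain the gap. With never-starters counted at 8 exercises and starters averaging 11, the exercise-weighted share is 8 × 0.207 / (8 × 0.207 + 11 × 0.793) = 16.0%.

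**2. When the two readings disagree.** Completion among all randomised = starters' rate × (1 − never-starter share). It stays at or above 70% while the share is at most 1 − 70/(starters' rate in %):

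| Starters' rate | Largest share | Of 24 |
|---|---|---|
| 76% (factorial trial) | 7.9% | 1.9 |
| 77% (PP arm of the first pilot) | 9.1% | 2.2 |
| 80% | 12.5% | 3.0 |
| 85% | 17.6% | 4.2 |

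The 77% is that pilot's reported PP-arm figure; the documents do not say whether never-starters are in it. At 76%, one never-starter gives 0.76 × 23/24 = 72.8% and two give 0.76 × 22/24 = 69.7%.

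**3. How often they would disagree.** Simulation with 24 participants, 12 exercises each, and starters' completion drawn from a beta distribution; the result counted is that starters-only passes while all-randomised fails. With starters at 76% (SD 0.20 to 0.30) this happens in 19–23% of trials at 5% never-starters and 39–47% at 10%. With 5% never-starters (SD 0.25) it falls to about 13% if starters complete 80%, and to roughly 4% if they complete 85%.

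**4. What the wording says.** Section I.B uses the phrase about all exercises twice. Standing alone, it gives 64% and covers everyone. The 76% comes only after a clause that removes those who dropped out before completing any exercise. Sections II and VI use the phrase with no such clause.

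**5. The other two conditions.** An all-enrolled denominator can be ruled out as intended: with 80 enrolled and 48 randomised, the most that could be reached is 48/80 = 60%, below both thresholds. For all 48 randomised, 85% needs 41 (0.85 × 48 = 40.8) and 80% needs 39 (0.80 × 48 = 38.4). The week can matter. If true self-report retention is 90% at week 12 and 85% at week 24 (assumed, with losses permanent), the 85% condition passes at week 12 and fails at week 24 in 33% of trials. That figure is 11% if week-24 retention is 88%, and 55% if it is 82%.

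**The case for a change.** The best case for a change is that the team applies the same words to both 64% and 76%, so the words alone do not fix who is counted. The condition is a yes-or-no rule on the primary aim. Even with only 5% never-starters, the two readings part in about one trial in five at the earlier starters' rate. A few sentences would close the gap at no cost, and completion and follow-up rates also feed the early review in Section IX.C.

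Part of this stands. No sentence states the rule for never-starters, names the week for the second and third conditions, or defines full. Randomisation at the return visit does not remove never-starters either, since the first exercise is assigned there and reviewed by phone a week later.

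The rest is weaker. The 76% is never given without its exclusion clause, so the unqualified phrase has a default meaning, and it is the stricter one. The factorial rates were interim and came from an eight-arm trial with a different schedule. Section VIII.B says the data will allow a larger trial, but does not make these thresholds a gate to it. The review in Section IX.C is a matter of judgement: it looks for rates far below expectation, and also for dissatisfaction that the team merely senses. A denominator rule would alter little there.

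**Conclusion.** The concern does not call for a change. Read as the team itself uses the phrase, the first condition covers all exercises assigned to everyone randomised to PP-MI, with uncompleted ones counted as not completed. That is the sound denominator and the harder one to pass. A clarification would write down a choice that the text already favours; it would not correct a wrong rule.

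The choice of reading would matter only if more than about 8% of the arm never start while starters complete 76%, which is two or more people in an assumed arm of 24. The margin widens to 12.5% if starters complete 80%. Assignment after the baseline questionnaires, just before the first session, lets some early loss fall before randomisation, though the documents do not show how much.

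The open week and the undefined full data are gaps that analysts fill sensibly. Participants, with no arm named, most naturally means all those randomised. Both weeks are collected and both rates can be tabulated by arm. The 5-day, 8-hour standard is at hand as a wear rule, provided the report says it was used. For a descriptive pilot aim, a report that shows these rates with their denominators lets any reader apply the thresholds.
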